## 6.11 Safety Analyses

The safety analyses will be presented by the treatment received for the Safety Analysis Set.

### 6.11.1 Adverse Events

Subjects will be monitored continuously for any AEs from the time of informed consent through the end of the study. Only treatment emergent adverse events (TEAE) will be summarized. All AEs will be listed. TEAEs will be presented by treatment panel (Fed/Fasted) and overall.

A TEAE is defined as:

- Any AE that has an onset on or after the first dose of study drug through the EOS/EW follow-up visit.
- Any pre-existing AE that has worsened in severity on or after the first dose through the EOS/EW follow-up visit.

Relatedness of an AE to treatment can be classified as Not Related, Unlikely, Possible, Probable or Certain. A treatment-related AE is defined as any AE classified as possibly, probably or certainly related to the study drug. If an AE has missing relationship it is assumed to be related to the study drug for analysis purposes.

Severity of AEs will be graded using the Division of Microbiology and Infectious Disease (DMID) Toxicity Grade November 2007 version: Grade 1 (Mild), Grade 2 (Moderate), Grade 3 (Severe), Grade 4 (Potentially Life-Threatening). Maximum grade will be assumed for an AE with missing grade.

The following tables will be presented for AEs:

- Overall incidence and number of TEAEs, Treatment-related TEAEs, SAEs, Treatment-related SAEs, TEAEs leading to Early Withdrawal and TEAEs leading to Death.
- TEAEs by system organ class and preferred term, incidence and number of events
- Treatment-related TEAEs by system organ class and preferred term, incidence and number of events
- TEAEs by system organ class, preferred term and maximum grade, incidence
- TEAEs by system organ class, preferred term and relationship, incidence
- Listing of AEs Leading to Early Withdrawal (presented in the Table section of the appendices)
- Listing of Serious AEs (presented in the Table section of the appendices)

QMD Ref: Worldwide-TMP-ST-006-4.0 Effective: 12Aug2019	Governing QMD: Worldwide-SOP-ST-001
Confidentiality Statement This document is the property of Worldwide Clinical Trials Inc. and may not be duplicated, copied, altered or removed from company without prior approval from Worldwide Quality Assurance or in compliance with Worldwide Standard Operating Procedures.	

Worldwide Clinical Trials Controlled Quality Management Document		
 WORLDWIDE CLINICAL TRIALS	Sponsor: Protocol Number:	TB Alliance Pa-824-CL-011
STATISTICAL ANALYSIS PLAN – PHASE 1		

- Listing of Deaths (presented in the Table section of the appendices)

System organ class will be presented in descending order of overall frequency and then alphabetically. Preferred terms will be displayed in descending order of overall frequency and then alphabetically.

In counting the number of AEs reported, a continuous event (i.e. reported more than once and which did not cease), will be counted only once; non-continuous AE reported several times by the same subject will be counted as multiple events.

Where a subject reports more than one AE per system organ class and preferred term they will only be counted once for the most severe event or the most related event.

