## 1 INTRODUCTION

This document details the planned statistical analyses for TB Alliance, protocol “Pa-824-CL-011” study titled “An Open-label, Randomized, Four-period Crossover Study in Two Panels of Healthy Adult Participants to Assess the Relative Bioavailability, Food Effect, and Dose-dependence of Single-Dose Immediate-Release and Single-dose Dispersible Formulations of Pretomanid”. The proposed analyses are based on the contents of the final version of the protocol (dated 06-Dec-2019).

This is a single-dose, open-label, randomized, four-period, four-treatment, crossover study in healthy adult subjects. Each panel of 24 subjects will be randomized according to the same 4-sequence, 4-period Williams design, in which each participant will receive four single-dose treatments. Subjects in Panel 1 will receive all treatments after consuming an FDA standard high-fat, high-calorie breakfast following an overnight fast of at least 10 hours. Subjects in Panel 2 will receive all treatments directly following an overnight fast of at least 10 hours. The two panels will be investigated concurrently. The maximum duration of the study from screening to study exit will be approximately 54 days.

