### 2.2 Secondary Objectives

The secondary objectives of the study are as follows:

- To determine the food effect for each of the formulations.
- To assess the effect of dose on the bioavailability of the dispersible pediatric formulation under fed and fasted conditions.
- To evaluate the taste perception of the dispersible pediatric formulation under fed and fasted conditions.
- To evaluate the short-term safety and tolerability for each of the formulations under fed and fasted conditions.

QMD Ref: Worldwide-TMP-ST-006-4.0 Effective: 12Aug2019	Governing QMD: Worldwide-SOP-ST-001
Confidentiality Statement This document is the property of Worldwide Clinical Trials Inc. and may not be duplicated, copied, altered or removed from company without prior approval from Worldwide Quality Assurance or in compliance with Worldwide Standard Operating Procedures.	

Worldwide Clinical Trials Controlled Quality Management Document		
 WORLDWIDE CLINICAL TRIALS	Sponsor: Protocol Number:	TB Alliance Pa-824-CL-011
STATISTICAL ANALYSIS PLAN – PHASE 1		

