## 6.8 Prior and Concomitant Medications

A listing of prior and concomitant medications will be provided. Prior medications are defined as all medications starting and stopping before the date of first dose of study drug. Concomitant medications are defined as medications taken on or after the date of first dose of study drug. Each concomitant medication will be assigned to the last study drug taken prior to starting the concomitant medication. Concomitant medications taken before the first dose of study drug will be assigned to 'No Treatment'. Prior and concomitant medications will be coded using the World Health Organization (WHO) Drug Dictionary B3 – September 2019 version.

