## 6.9 Exposure to Study Drug

Exposure to study medication will be tabulated by treatment panel and treatment group. All dosing information will be listed.

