### 6.11.2 Laboratory Data

Descriptive statistics of the observed values and change from baseline in Period 1 to end of each treatment period (continuous data) will be presented by treatment panel and treatment group for each hematology, urinalysis and serum chemistry parameter. Each measurement (continuous data) will be classed as below, within, or above normal range, based on ranges supplied by the laboratory used. Shift tables in relation to the normal range from baseline in Period 1 to the end of each treatment period will be presented. Descriptive statistics and normal range shift tables from baseline in Period 1 to EOS/EW will also be presented overall for each treatment panel. Values will be summarized using the original units as provided by the analytical laboratory.

A listing of any clinically significant laboratory measurements recorded throughout the study will also be presented. Other laboratory data including serology, urine drug, cotinine and alcohol screening and pregnancy test data will be listed.

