#### **6.11.6 Taste Evaluation**

Taste, Mouthfeel and Smell will be evaluated using the following categories: 1 - Like extremely, 2 - Like moderately, 3 - Neither like nor dislike, 4 - Dislike moderately and 5 - Dislike extremely.

QMD Ref: Worldwide-TMP-ST-006-4.0 Effective: 12Aug2019	Governing QMD: Worldwide-SOP-ST-001
Confidentiality Statement This document is the property of Worldwide Clinical Trials Inc. and may not be duplicated, copied, altered or removed from company without prior approval from Worldwide Quality Assurance or in compliance with Worldwide Standard Operating Procedures.	

Worldwide Clinical Trials Controlled Quality Management Document		
 WORLDWIDE CLINICAL TRIALS	Sponsor:	TB Alliance
	Protocol Number:	Pa-824-CL-011
STATISTICAL ANALYSIS PLAN – PHASE 1		

Taste evaluation will be summarized at each timepoint by treatment panel and treatment group.  
All data will be listed.

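### SAP 6.11.1 presents adverse events by fed/fasted panel only, against the by-treatment rule in 6.11, and no rule assigns an event to a treatment

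*SAP*

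**What the plan says.** Section 6.11 of the SAP opens with a general rule: "The safety analyses will be presented by the treatment received for the Safety Analysis Set". Section 6.11.1, which governs the adverse event tables, then says "TEAEs will be presented by treatment panel (Fed/Fasted) and overall". It does not mention treatment group.

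The design is a crossover within each panel, "in which each participant will receive four single-dose treatments". The secondary objective that the safety tables serve is "To evaluate the short-term safety and tolerability for each of the formulations under fed and fasted conditions" (SAP 2.2).

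Other sections name both dimensions:

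- Exposure (6.9): "Exposure to study medication will be tabulated by treatment panel and treatment group".
- By-period laboratory statistics (6.11.2): "will be presented by treatment panel and treatment group for each hematology, urinalysis and serum chemistry parameter".
- Taste (6.11.6): "Taste evaluation will be summarized at each timepoint by treatment panel and treatment group".

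Vital signs by period (6.11.3) are specified the same way. For concomitant medications, section 6.8 gives an explicit attribution rule: "Each concomitant medication will be assigned to the last study drug taken prior to starting the concomitant medication". The adverse event section has no counterpart.

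**The concern.** The two sentences give different column structures for the same tables, and the more specific one leaves treatment out. If Tables 14.3.1.1 to 14.3.1.5 follow 6.11.1 as worded, each panel column mixes two formulations and three dose levels. No adverse event summary table would then address the objective of safety for each formulation under fed and fasted conditions.

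A second gap remains even if treatment columns are intended: nothing says which treatment an event belongs to. The treatment-emergent definition runs from the first dose of study drug to the end-of-study or early-withdrawal visit, so it does not tie an event to a period. The once-per-term subject count does not say whether it applies within a treatment or across the whole study.

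All adverse events are still listed, so no data are lost. What would be missing is a tabulated incidence by formulation and dose.

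**Working it through.** The plan gives no figure to reproduce here. The check is a comparison of texts, followed by exact counts to show what a pooled column hides.

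**1. Are panel and treatment group the same thing?** No. SAP 6.3 gives them separate display labels: panel is Fed or Fasted, and treatment group is one of the four products.

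**2. What does panel-and-overall wording mean elsewhere in the SAP?** Sections 6.4 (disposition) and 6.6.1 (demographics) use it for tables that have panel columns only. Where columns by treatment are wanted, the SAP says so (6.9, 6.11.2, 6.11.3, 6.11.6). Read consistently, 6.11.1 calls for pooled columns.

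**3. Is there an attribution rule anywhere?** None was found in SAP 6.2, 6.3, 6.8, 6.9 or 6.11, the table list in section 9, the SAP supplement, or protocol sections 5.8 and 6. The missing-date rule in SAP 6.2.5 settles only whether an event counts as treatment emergent. The supplement leaves the SAP text unchanged.

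**4. What does a panel column combine?** There are 24 subjects per panel (SAP section 4) and 4 treatments per subject.

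- Doses per panel: up to 24 x 4 = 96.
- Doses in the overall column: up to 2 x 96 = 192, in 24 + 24 = 48 subjects.

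**5. Can a pooled row be separated afterwards?** Take one adverse event term, all 24 subjects dosed with each treatment, one event per affected subject, and no cases in the other panel. The case counts are illustrative and do not come from the documents.

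| | Case 1: 8 subjects, all after B | Case 2: 2 different subjects after each treatment |
|---|---|---|
| A | 0/24 (0%) | 2/24 (8.3%) |
| B | 8/24 (33.3%) | 2/24 (8.3%) |
| C | 0/24 (0%) | 2/24 (8.3%) |
| D | 0/24 (0%) | 2/24 (8.3%) |
| Panel row | 8/24 (33.3%), 8 events | 4 x 2 = 8; 8/24 (33.3%), 8 events |
| Overall row | 8/48 (16.7%) | 8/48 (16.7%) |

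The panel and overall rows are identical in the two cases, and the event count does not separate them either. In general, if 8 of 24 subjects have the event after at least one treatment, the number with it after any one named treatment can be anything from 0 to 8, that is 0% to 33.3%.

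**The case against.** The strongest reply is that 6.11.1 should be read together with its parent section and with SAP 6.3, which says clinical summaries are given by panel and treatment group, or overall. On that reading, 6.11 supplies the treatment columns and 6.11.1 only adds the fed/fasted split and totals. The reading is possible, but the text does not settle it: the 6.3 convention allows an overall presentation as an alternative, and 6.4 and 6.6.1 use the 6.11.1 phrasing for panel-only tables. Even if it is accepted, the attribution rule and the denominators are still missing.

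Several further points stand and limit the finding:

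- Table columns are fixed by the shells. The SAP has a shell approval part, but the shells are not in the text available for review and may show treatment columns. The adverse event table titles in section 9 name neither panel nor treatment columns, so they do not decide the matter.
- The 8/24 and 2/24 counts show that a pooled row cannot be separated. They do not predict what this trial would find.
- Attribution to the last dose is easy to derive. Each period has one dose, doses are 7 days apart (protocol section 3), subjects are confined to Day 26 (protocol 5.3), and onset dates are recorded (protocol 6.3.1).
- Laboratory, vital sign and taste data are by treatment group, so the tolerability objective does not rest on the adverse event tables alone.
- SAP section 6 allows additional tables in the study report if the justification is documented.

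These points make the problem cheap to correct. They do not remove the conflict between 6.11 and 6.11.1.

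**Conclusion.** The concern holds. SAP 6.11 and 6.11.1 contradict each other on how treatment-emergent events are presented. Taken at its word, 6.11.1 pools A, B, C and D within each panel and leaves no adverse event incidence table that answers the per-formulation safety objective. In the illustration, a panel row of 8/24 is compatible with anything from 0% to 33.3% for a given treatment.

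The conclusion concerns the SAP wording. Whether the produced tables pool treatments depends on the shells, which could not be checked. The missing attribution rule does not depend on which reading of 6.11.1 is adopted. The adverse event analysis is descriptive, and no pharmacokinetic or primary result is affected. The correction should be made.

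**What to change.** Amend 6.11.1 to agree with 6.11, along these lines:

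- Present treatment-emergent events by panel and treatment group, with panel and overall totals.
- Use as the denominator for each treatment column the subjects dosed with that treatment in that panel.
- Assign each event to the most recent study dose before onset or, for a pre-existing event, before worsening. This follows the rule in 6.8.
- Apply the once-per-term subject count within treatment for treatment columns, and within subject for totals.
- Keep the present rule that a continuous event is counted once.
- State how an event with a missing onset is assigned. Section 6.2.5 expects no missing dates, so this should rarely matter.

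Apply this to Tables 14.3.1.1 to 14.3.1.5 and confirm that the shells match. The SAP supplement shows that the database is already locked. The by-treatment tables can therefore be documented openly in the study report as additional tables, as SAP section 6 permits.

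The cost is SAP wording and wider tables; onset and dosing data are already collected. There are small drawbacks. An event starting late in a washout is attributed to the preceding dose. A continuous event that runs past the next dose stays under the earlier treatment. Subject counts across treatment columns can add to more than the panel total, because one subject can have the same term after more than one treatment.

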### 6.11.2 Laboratory Data

Descriptive statistics of the observed values and change from baseline in Period 1 to end of each treatment period (continuous data) will be presented by treatment panel and treatment group for each hematology, urinalysis and serum chemistry parameter. Each measurement (continuous data) will be classed as below, within, or above normal range, based on ranges supplied by the laboratory used. Shift tables in relation to the normal range from baseline in Period 1 to the end of each treatment period will be presented. Descriptive statistics and normal range shift tables from baseline in Period 1 to EOS/EW will also be presented overall for each treatment panel. Values will be summarized using the original units as provided by the analytical laboratory.

A listing of any clinically significant laboratory measurements recorded throughout the study will also be presented. Other laboratory data including serology, urine drug, cotinine and alcohol screening and pregnancy test data will be listed.

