**Figure 1 Trial Schematic**

Session I (Days 1-5)	Days 6, 7	Session II (Days 8-12)	Days 13, 14
Panel 1: Treatment A, B, C or D (single dose) with breakfast  or  Panel 2: Treatment A, B, C or D after a 10-hour overnight fast	2-day break	Panel 1: Treatment A, B, C or D (single dose) with breakfast  or  Panel 2: Treatment A, B, C or D after a 10-hour overnight fast	2-day break
Session III (Days 15-19)	Days 20, 21	Session IV (Days 22-26)	Follow-up Visit (Day 33)
Panel 1: Treatment A, B, C or D (single dose) with breakfast  or  Panel 2: Treatment A, B, C or D after a 10-hour overnight fast	2-day break	Panel 1: Treatment A, B, C or D (single dose) with breakfast  or  Panel 2: Treatment A, B, C or D after a 10-hour overnight fast	7 days after last PK sample in Session IV

The screening period will begin within 21 days of the first participant being dosed. Subjects will be assigned numbers in an ascending order, based on successful completion of the screening process.

Subjects will receive a single dose of each treatment listed in [Table 1](#) in randomized fashion during the four treatment periods.

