**Table 1: Treatment Schedule**

Sequence (n=24 subjects per panel)	Treatment Periods			
	Period 1	Period 2	Period 3	Period 4
ABCD	A	B	C	D
BDAC	B	D	A	C
CADB	C	A	D	B
DCBA	D	C	B	A

Treatment A (reference) = 200 mg given as a single 200 mg tablet (using the immediate release formulation), orally administered.

Treatment B (test) = 200 mg given as four 50-mg tablets (using the dispersible pediatric formulation), orally administered.

Treatment C (test) = single 50-mg dispersible tablet, orally administered.

Treatment D (test) = single 10-mg dispersible tablet, orally administered.

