### 6.2.2 Baseline

For variables that will be summarized by treatment, the baseline for each period is defined as the last non-missing value (either scheduled, unscheduled or repeat) that is collected before dosing, but after check-in for the relevant period.

For variables that will be summarized overall, baseline is defined as the last non-missing value (either scheduled, unscheduled or repeat) that is collected before the subject receives the first dose of study drug.

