### 6.11.3 Vital Signs

Descriptive statistics for observed values and change from baseline within the relevant treatment period will be presented by treatment panel and treatment group for all scheduled measurements of the following vital signs:

- Systolic blood pressure (mmHg)
- Diastolic blood pressure (mmHg)
- Pulse rate (bpm)
- Respiration rate (breath/min)
- Body temperature (degrees Celsius)

QMD Ref: Worldwide-TMP-ST-006-4.0 Effective: 12Aug2019	Governing QMD: Worldwide-SOP-ST-001
Confidentiality Statement	

This document is the property of Worldwide Clinical Trials Inc. and may not be duplicated, copied, altered or removed from company without prior approval from Worldwide Quality Assurance or in compliance with Worldwide Standard Operating Procedures.

Worldwide Clinical Trials Controlled Quality Management Document		
 WORLDWIDE CLINICAL TRIALS	Sponsor: Protocol Number:	TB Alliance Pa-824-CL-011
STATISTICAL ANALYSIS PLAN – PHASE 1		

- Body weight (kg)
- Pulse oximetry (%)

The change from baseline in Period 1 to EOS/EW will also be summarized overall. All vital sign data will be listed.

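### SAP 6.11.2 reports laboratory change by treatment from the Period 1 baseline, although SAP 6.2.2 sets a same-period baseline for by-treatment summaries and states no exception

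*SAP*

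**What the plan says.** SAP 6.2.2 defines two baselines:

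- By treatment: "For variables that will be summarized by treatment, the baseline for each period is defined as the last non-missing value", and that value must be "collected before dosing, but after check-in for the relevant period".
- Overall: "For variables that will be summarized overall, baseline is defined as the last non-missing value" before the first dose of study drug, which is in effect the Period 1 baseline.

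SAP 6.11.2 states that laboratory "change from baseline in Period 1 to end of each treatment period (continuous data) will be presented by treatment panel and treatment group". It adds: "Shift tables in relation to the normal range from baseline in Period 1 to the end of each treatment period will be presented". The by-treatment layout is explicit for the change. The shift-table sentence gives no layout.

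SAP 6.11.3 takes the other route for vital signs: "change from baseline within the relevant treatment period will be presented by treatment panel and treatment group". It keeps the Period 1 baseline for the overall change to the end-of-study or early-withdrawal visit, as 6.2.2 provides.

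The protocol synopsis plans laboratory tests before every dose and again at 96 hours. Protocol 5.3 has subjects admitted once, on Day -1, and kept in the unit until Day 26.

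**The concern.** The two SAP sections do not give a programmer a single laboratory baseline. If 6.11.2 is followed as written, a change placed under one treatment label also covers every treatment given since the start of the study, together with anything that moves over the weeks of confinement. Haemoglobin is a plausible case: pharmacokinetic sampling alone takes 120 mL over the study (Protocol 5.6), and Protocol 1.1 itself reports that falls in haemoglobin came mainly from a study with repeated blood draws.

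At stake is the secondary objective of describing short-term safety for each formulation. A cumulative change is not specific to the treatment named at the head of its column. The laboratory and vital-sign tables would also use the words change from baseline, by treatment, in two different senses.

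**Working it through.** The plan states no figure on this point, so there is none to reproduce. The check is a count over the planned design.

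**Inputs**
- Sequences ABCD, BDAC, CADB and DCBA, with the header "Sequence (n=24 subjects per panel" (SAP Table 1).
- Subjects per sequence: not stated. Assumed equal, 24/4 = 6, all completing.
- Doses: A 200 mg, B 200 mg, C 50 mg, D 10 mg.
- Sessions on Days 1-5, 8-12, 15-19 and 22-26; the last is shown as "Session IV (Days 22-26" (Protocol Figure 1).

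**Earlier treatments inside the interval.** Each treatment occurs once in each of positions 1 to 4. Per treatment per panel, 6 subjects therefore have 0 earlier treatments, 6 have 1, 6 have 2 and 6 have 3. With at least one: 6 + 6 + 6 = 18 of 24 (75%). Under the 6.2.2 baseline the number is 0 of 24. In the three unequal splits tried (7/6/6/5, 5/6/6/7 and 8/6/5/5) it ranges from 16 to 19 of 24.

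**Earlier dose inside the interval (mg), by sequence**

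| Treatment | ABCD | BDAC | CADB | DCBA | Mean |
|---|---|---|---|---|---|
| A | 0 | 210 | 50 | 260 | 520/4 = 130 |
| B | 200 | 0 | 260 | 60 | 520/4 = 130 |
| C | 400 | 410 | 0 | 10 | 820/4 = 205 |
| D | 450 | 200 | 250 | 0 | 900/4 = 225 |

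The design balances the number of earlier treatments across A to D, but not the earlier dose. The 10-mg column carries the most: 225 mg on average, against 10 mg of its own.

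**Length of the interval to the 96-hour sample**
- From a Day 1 pre-dose sample: 5-1 = 4, 12-1 = 11, 19-1 = 18, 26-1 = 25 days; mean 58/4 = 14.5.
- From the Day -1 check-in sample of Protocol 5.2, one day earlier: 5, 12, 19 and 26 days; mean 62/4 = 15.5.
- A same-period change from a dosing-day sample: 4 days.

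**Do the same-period samples exist?** The synopsis says that they do. Protocol 5.2 describes laboratory collection at Day -1 only, and 5.8.2 defers to Table 5, whose laboratory row could not be read in the copy available. Protocol 5.6 gives about 87.5 mL for laboratory tests. That equals 7 draws of 12.5 mL (screening, Day -1, Days 5, 12, 19, 26 and 33) or, with Days 8, 15 and 22 added, 10 draws of 8.75 mL. Equal draw volumes are an assumption, so this is suggestive at most.

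**The case against.** The best defence is that 6.11.2 is a deliberate, specific rule that overrides a general definition. It names the Period 1 baseline for the change, the shifts and the end-of-study summary, while 6.11.3 names the treatment period and 6.11.4 distinguishes the two baselines for ECG data. If laboratory samples are not taken before dosing in Periods 2 to 4, the Period 1 baseline may be the only one available. This reading is possible, but the SAP does not state it. Even if it is right, 6.2.2 needs the exception, and the table needs a label that does not present the change as treatment-specific.

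It is also fair to say that 18 of 24 counts intervals, not error. Any Period 1 baseline in a balanced four-period crossover gives that count. A reader might infer that the by-treatment laboratory results will be materially distorted, or that the same-period baseline is always the better one. The documents support neither. They say nothing about how long a laboratory effect lasts. With equal sequences, drift common to all subjects falls equally on the four treatments. A same-period change can itself be wrong if an earlier effect is still resolving at the next dose.

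Finally, individual safety review does not depend on these tables: Protocol 6.7 has the investigator judge each abnormal result against the subject's own baseline, and clinically significant values are listed. That stands, and it keeps the point small.

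**Conclusion.** The inconsistency between SAP 6.2.2 and 6.11.2 is real and should be corrected, as a minor point. With equal sequences and all subjects completing, the laboratory change covers one to three earlier treatments in 18 of 24 subjects per treatment per panel, over up to 25 days (26 from Day -1). Confidence is high in the wording conflict and the count. It is lower in the preferred remedy, because pre-dose laboratory samples in Periods 2 to 4 rest on the synopsis alone. It would go too far to say that those samples are missing, or that the shift tables are planned by treatment: the documents settle neither. Observed values by treatment, the listings and all pharmacokinetic analyses are unaffected, and the size of any error in the change tables cannot be estimated from the documents.

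The 6.2.2 rule has a related gap. The condition "collected before dosing, but after check-in for the relevant period" has no clear meaning in Periods 2 to 4 under the single admission and continuous stay of Protocol 5.3, yet Protocol 5.4.1 speaks of check-in as if it recurred. This affects vital signs as well.

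**What to change.** 1. Confirm from Protocol Table 5 whether laboratory samples are taken before dosing in Periods 2 to 4, as the synopsis states.
2. If they are: in 6.11.2, present by-treatment laboratory change (and shifts, if shown by treatment) from the same-period pre-dose value to that period's 96-hour value. Keep the change from the Period 1 baseline in a table by study period, labelled cumulative, and in the overall end-of-study or early-withdrawal summary. Footnote that a same-period change can also be affected when an earlier effect has not resolved.
3. If they are not: name laboratory data as an exception in 6.2.2, and show the Period 1 change by study period, labelled cumulative, rather than under treatment labels.
4. In either case, reword the check-in condition in 6.2.2 so that it works with one admission, for instance by requiring a value later than the last assessment of the preceding period (in Period 1, later than the Day -1 check-in). Reconcile Protocol 5.4.1 with 5.3.

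The cost is SAP wording, a baseline flag and at most one extra set of descriptive tables. No new samples are needed: if the pre-dose samples are not taken, step 3 requires only wording and relabelling.
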